Appendix Table 7. Schedule of Treatment Administration for MEC – Cohort 2 (R/R AML Mag+MEC)

		1				2 to 3 ^b											
Cycle Day ^a	1	2	3	4	5	8	11	15	22	1	2	3	4	5	8	15	22
Visit Window (days)	0				±	3	•	•				•	±	3			•
Mitoxantrone	X	X	X	X	X					X	X	X	X	X			
Etoposide	X	X	X	X	X					X	X	X	X	X			
Cytarabine	X	X	X	X	X					X	X	X	X	X			

AML = acute myeloid leukemia; MEC = mitoxantrone, etoposide, cytarabine; R/R = relapsed/refractory

Appendix Table 8. Schedule of Treatment Administration for CC-486 – Cohort 3 (Post-Chemo Maint Mag+CC-486)

	Cycle (28-day Cycles)										
			-	1				3+			
Cycle Day ^a	1	4	8	11	15	22	1	8	15	22	1
Visit Window (days)	0	± 3					±	: 3		± 3	
CC-486		Daily Days 1-14					Daily Days 1-14			Daily Days 1-14	

CC-486 = Onureg

a Adverse events and concomitant medications should be recorded at all scheduled and unscheduled assessment visits, and at all treatment visits, even when other assessments are not scheduled.

b If patient achieved blast clearance after Cycle 1, one additional cycle of MEC will be given (total 2 cycles). If patient achieved blast clearance only after Cycle 2, a third cycle of MEC will be given. If no blast clearance at the end of Cycle 2, patient should be discontinued from the study.

a Adverse events and concomitant medications should be recorded at all scheduled and unscheduled assessment visits, and at all treatment visits, even when other assessments are not scheduled.

Appendix Table 9. Schedule of Assessments – Post Treatment

	End-of-treatment Visit	Safety Follow-up Visit/ Telephone Call ^a	Safety Follow-up Visit/ Telephone Call ^a	
	Within 7 Days after Last Dose or EOT Decision	30 Days after Last Dose	70 Days after Last Dose	
Visit Window (Days)	± 7	± 7	± 7	
Serum or urine pregnancy test ^b	Q4W		•	
CBC with differential, platelets, reticulocytes	X			
Serum or plasma chemistry	X			
Peripheral blood for correlative studies	X			
Pharmacokinetics	X			
Antidrug antibodies	X			
Bone marrow aspirate/biopsy for response assessment ^c , cytogenetics ^d , and MRD assessment	X			
Bone marrow aspirate/biopsy for correlative studies	X			
Peripheral blood smear (for blasts) ^e	X			
ECOG performance status	X			
Vital signs	X			
Symptom-directed physical examination	X			
Adverse events ^f	X	X	X	
Concomitant medications	X	X	X	
New anti-AML therapy reportingg	X	X	X	

AE = adverse event; AML = acute myeloid leukemia; CBC = complete blood count; ECOG = Eastern Cooperative Oncology Group; EOT = end of treatment; MRD = minimal residual disease; Q4W = every 4 weeks; SAE = serious adverse event

a If the patient experiences a treatment-related AE or an SAE (regardless of attribution), the patient must be asked to come to the site.

b Pregnancy testing will be continued monthly up to 6 months after the end of treatment per the duration of contraception requirement as discussed in Appendix 5. Testing after 70 days of safety follow-up may be done at home and the result self-reported by the patient.

c Response assessment at EOT visit not required if performed within the last 30 days or progressive disease has been documented.

d Conventional cytogenetics to be tested per institutional standards.

e Peripheral blood smears for blasts are to be collected along with bone marrow aspirate/biopsy.

f Report all AEs through the Safety Follow-up Visit/Call, and any treatment-related SAEs thereafter through the 70-day safety follow-up visit/call.

g Collect data for the first new anti-AML therapy following the last dose of study treatment.

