3.4. Discontinuation Criteria

Reasons for discontinuation of study treatment must include, but are not limited to, the following:

- Disease progression (including treatment failure and relapse)
- Unacceptable toxicity
- Loss of clinical benefit
- Death
- Pregnancy during the study

- Patient request, with or without a stated reason
- Patient noncompliance
- Initiation of anti-AML therapy
- SCT
- Investigator or treating physician decision
- Protocol violation
- Lost to follow-up
- Discontinuation of the study at the request of Gilead, a regulatory agency, or an institutional review board (IRB)/independent ethics committee (IEC)

Although disease progression is considered a sufficient reason for discontinuing a patient from study treatment, given the delayed treatment benefit commonly seen in immune therapies, the investigator is advised to continue to treat the patient until the investigator considers the study treatment to be no longer clinically beneficial to the patient, or the change of disease state renders the patient unacceptable for further treatment in the judgment of the investigator. All patients must be followed through completion of all study treatments.

If patients remain on study drugs beyond disease progression, a second bone marrow assessment, along with required laboratory tests for response assessment, should be done within 4 weeks. If disease progression is confirmed at the second bone marrow assessment, the patient should be discontinued from the study treatment.

Patients who discontinue study treatment are to return for an end-of-treatment (EOT) visit for evaluation of safety within 7 days (\pm 7 days) of their last dose or the decision to end study treatment, whichever is later. In addition, patients are to have a safety follow-up telephone call 30 days and 70 days (\pm 7 days) after their last dose of study treatment. When a serious adverse event (SAE) or treatment-related AE is reported during the telephone call, the patient should come to the clinic for physical examination and blood tests, if clinically needed. Follow-up for ongoing SAEs or treatment-related AEs after the safety follow-up visit/call will stop if a patient begins another anti-AML therapy.

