6.5.7. Adverse Events

At each visit, all AEs observed by the investigator or reported by the patient that occur after the first dose of study treatment through 70 days (± 7 days) after the last dose of study treatment are to be reported using the applicable eCRF (Section 7.1.1). Full details on the definitions, assessment, and reporting instructions for AEs are provided in Section 7.

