7.3.2. Adverse Events

Following initiation of study medication, all AEs, regardless of cause or relationship, will be collected until 70 days (± 7 days) after last administration of study drug and reported on the eCRFs as instructed.

All AEs should be followed up until resolution or until the AE is stable, if possible. Gilead may request that certain AEs be followed beyond the protocol-defined follow-up period.

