7.3.3. Serious Adverse Events

All SAEs, regardless of cause or relationship, that occur after the patient first consents to participate in the study (ie, signing the ICF) and throughout the duration of the study, including the posttreatment follow-up visit, must be reported on the applicable eCRFs and Patient Safety (PS) as instructed below in this section. This also includes any SAEs resulting from protocol-associated procedures performed after the ICF is signed.

Any SAEs and deaths that occur after the posttreatment follow-up visit but within 70 days (± 7 days) of the last dose of study drug, regardless of causality, should also be reported.

Investigators are not obligated to actively seek SAEs after the protocol-defined follow-up period; however, if the investigator learns of any SAEs that occur after the protocol-defined follow-up period has concluded and the event is deemed relevant to the use of study drug, the investigator should promptly document and report the event to Gilead PS.

Instructions for reporting SAEs are described in Section 7.4.1.

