8.6.2. Adverse Events

Clinical and laboratory AEs will be coded using the Medical Dictionary for Regulatory Activities (MedDRA). System organ class, high-level group term, high-level term, preferred term, and lower-level term will be attached to the clinical database.

Events will be summarized on the basis of the date of onset for the event. A treatment-emergent AE will be defined as any AE that begins on or after the date of first dose of study drug up to the date of last dose of study drug plus 70 days (\pm 7 days).

Summaries (number and percentage of patients) of treatment-emergent AEs (by system organ class and preferred term) will be provided by treatment group.

Adverse events that occurred before exposure to study treatment will be reported in data listings and appropriately identified as non-treatment-emergent AEs.

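### Appendix Table 9 footnote f narrows AE reporting between the 30-day and 70-day contacts to treatment-related SAEs, contradicting Sections 6.5.7, 7.3.2, 7.3.3 and the TEAE window in 8.6.2

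*Protocol*

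**What the plan says.** Appendix Table 9 has three post-treatment columns: the end-of-treatment visit, a safety follow-up visit or call headed "30 Days after Last Dose", and a second such contact at 70 days. The adverse event row is marked in all three. Its footnote f states: "Report all AEs through the Safety Follow-up Visit/Call, and any treatment-related SAEs thereafter through the 70-day safety follow-up visit/call". Section 3.4 describes the same two contacts: "patients are to have a safety follow-up telephone call 30 days and 70 days", with a window of 7 days either way.

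The body of the protocol sets a wider collection rule:

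- Section 6.5.7 covers all AEs that "occur after the first dose of study treatment through 70 days (± 7 days) after the last dose of study treatment".
- Section 7.3.2 states that "all AEs, regardless of cause or relationship, will be collected until 70 days (± 7 days) after last administration of study drug".
- Section 7.3.3 adds serious events, again whatever their cause: "Any SAEs and deaths that occur after the posttreatment follow-up visit but within 70 days" of the last dose are also to be reported.

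The analysis follows the wider rule. Section 8.6.2 defines a treatment-emergent AE as one starting from first dose "up to the date of last dose of study drug plus 70 days" (± 7 days). Sections 8.3.1.2 and 8.6 summarise safety data over the same period.

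**The concern.** The footnote and the body text give a site two different instructions for the same weeks, and the analysis assumes the wider one was followed. An event that a site does not record because the footnote excludes it cannot be recovered at analysis.

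The outcome exposed is TEAE incidence. Section 8.1.2 makes it part of the primary endpoint for the safety run-in cohorts, and Section 8.1.3 makes it the secondary safety endpoint for the Phase 2 cohorts. If some sites work from the schedule and others from Section 7, the late part of the incidence reflects which page was read as well as what happened to patients. The loss would also be selective: it removes non-serious events and those SAEs that the investigator judged unrelated.

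**Working it through.** The plan states no figure on this point, so there is none to reproduce. The check compares texts and then measures the disputed period.

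**Step 1: which contact footnote f means.** Two columns carry the safety follow-up title. If the footnote's first clause meant the 70-day contact, its second clause, which runs from that contact to the 70-day contact, would cover no time. The first clause must therefore mean the 30-day contact.

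**Step 2: what each rule requires between the 30-day and 70-day contacts.**

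| Event | Footnote f | Sections 6.5.7, 7.3.2, 7.3.3 | Counted under 8.6.2 |
|---|---|---|---|
| Non-serious AE, related | Not reported | Reported | Yes |
| Non-serious AE, unrelated | Not reported | Reported | Yes |
| SAE, related | Reported | Reported | Yes |
| SAE, unrelated (including deaths not due to AML progression) | Not reported | Reported | Yes |

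The rules agree on one row of four. Progression of AML and deaths related to it, when assessed as unrelated to study drug, are outside AE reporting under Section 7.1.2.1, so they are not in dispute.

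**Step 3: whether the document settles which rule prevails.** It does not, and several passages point towards the table. Sections 3.6 and 6.12 say that AE follow-up after treatment is as specified in Appendix Table 9. Section 9.1.7 says the eCRF casebook captures only what the schedules of assessments require. The schedule thus governs what is captured, while Section 8.6.2 governs what is counted.

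**Step 4: length of the disputed period.** Inputs are the two contact days (30 and 70) and their ± 7-day windows, all from Appendix Table 9.

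- Nominal: 70 − 30 = 40 days; 40/70 = 57% of the post-dose window.
- Shortest (30-day contact late, 70-day contact early): 63 − 37 = 26 days; 26/63 = 41%.
- Longest (30-day contact early, 70-day contact late): 77 − 23 = 54 days; 54/77 = 70%.

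These are shares of calendar time after last dose, not of events. Turning them into events would need a post-treatment AE rate, which the protocol does not give.

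**The case against.** The strongest reply is that one footnote stands against several explicit sections, and that the table itself partly supports the wider rule. The adverse event row is marked at 70 days. Footnote a has a patient with a treatment-related AE, or an SAE whatever its attribution, asked to come to the site. Section 7.1.2.1.1 separately requires deaths not due to AML progression to be recorded during the AE reporting period, and Section 7.4.1.1 requires SAE transmission through post-treatment follow-up. Many sites may therefore collect everything.

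This has force against a prediction. A reader might infer that sites will record next to nothing after the 30-day contact. The documents do not support that, because the Day 70 mark and footnote a pull the other way and footnote f itself keeps related SAEs. What stands is that under-collection can occur. The reply does not remove the contradiction, given the cross-references in Sections 3.6, 6.12 and 9.1.7.

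A reader might also infer that dose selection is compromised. It is little affected: Section 3.1.1.1 sets the DLT period at 28 days from the start of treatment, extended to 42 days for prolonged myelosuppression in Cohorts 1 and 2, and Section 8.3.1.2 bases the RP2D on the DLT Evaluable Analysis Set.

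Finally, a reader might see a further error in the TEAE window continuing past transplant or new anti-AML therapy, or in its ± 7 days. No passage contradicts Section 8.6.2 on the first, and both are analysis conventions commonly settled in the SAP, which is not at hand. A cut-off at new therapy would also move late toxicity of study treatment out of the TEAE tables.

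**Conclusion.** The contradiction is real and unresolved in the protocol. Between the 30-day and 70-day contacts, footnote f asks only for treatment-related SAEs, while the reporting sections ask for all AEs, SAEs and deaths not due to AML progression, and the TEAE definition counts them. The disputed period is nominally 40 of the 70 post-dose days, with a range of 26 of 63 to 54 of 77 when the visit windows are taken at their extremes.

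The consequence is that TEAE incidence can be under-collected and can differ between sites. This assumes that at least some sites, or the eCRF build, follow the footnote; the protocol does not show how many. The number of missing events is unknown. As a share of a patient's whole treatment-emergent window, the gap also depends on time on treatment, so no single percentage of that kind describes the trial. The exposure is confined to the TEAE summaries and scarcely reaches DLTs or the RP2D.

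**What to change.** Reconcile footnote f with Sections 6.5.7, 7.3.2, 7.3.3 and 8.6.2. The simplest change is to replace it with one instruction: all AEs and SAEs, irrespective of relationship to study drug, are reported through the 70-day safety follow-up contact. The collection window then matches the TEAE analysis window, and Sections 3.6, 6.12 and 9.1.7 can continue to point to the table. The eCRF completion guidance should be checked for the same restriction.

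The cost is one footnote and a notice to sites. The 70-day contact is already scheduled and the adverse event row already marked there, so no visit or procedure is added. For patients already past their 30-day contact, sites can be asked whether events were left out because of the footnote. The TEAE definition in Section 8.6.2 need not change for this purpose.

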9.1.7. Case Report Forms

For each patient consented, an eCRF casebook will be completed by an authorized study staff member whose training for this function is completed in the electronic data capture (EDC) system. The eCRF casebook will only capture the data required per the protocol schedules of assessments. The Inclusion/Exclusion Criteria and Enrollment eCRFs should be completed only

after all data related to eligibility have been received. Data entry should be performed in accordance with the CRF Completion Guidelines provided by the sponsor. Subsequent to data entry, a study monitor will perform source data verification within the EDC system. System-generated or manual queries will be issued in the EDC system as data discrepancies are identified by the monitor or Gilead staff who routinely review the data for completeness, correctness, and consistency. The site investigator, site coordinator, or other designee is responsible for responding to the queries in a timely manner, within the system, either by confirming the data as correct or updating the original entry, and providing the reason for the update (eg, data entry error). Original entries as well as any changes to data fields will be stored in the audit trail of the system. At a minimum, prior to any interim time points or database lock (as instructed by Gilead), the investigator will use his/her log-in credentials to confirm that the forms have been reviewed, and that the entries accurately reflect the information in the source documents. At the conclusion of the study, Gilead will provide the site investigator with a read-only archive copy of the data entered by that site. This archive must be stored in accordance with the records retention requirements outlined in Section 9.1.6.

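### Appendix Table 9 footnote f narrows AE reporting after the first safety call to treatment-related SAEs, contradicting the rules that require all AEs and SAEs to Day 70

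*Protocol*

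**What the plan says.** Appendix Table 9 (post-treatment schedule) has an end-of-treatment visit and two identically named safety follow-up columns, headed "30 Days after Last Dose" and "70 Days after Last Dose", each with a ±7-day window. Section 3.4 confirms the pair: "patients are to have a safety follow-up telephone call 30 days and 70 days". The adverse-event row is ticked in all three columns and carries footnote f: "Report all AEs through the Safety Follow-up Visit/Call, and any treatment-related SAEs thereafter through the 70-day safety follow-up visit/call".

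The body text sets a different rule:

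- Section 6.5.7 has all AEs after first dose reported on the eCRF to 70 days (±7) after last dose.
- Section 7.3.2: "all AEs, regardless of cause or relationship, will be collected until 70 days" (±7) after last administration.
- Section 7.3.3: "Any SAEs and deaths that occur after the posttreatment follow-up visit but within 70 days" (±7) of last dose are also reportable, irrespective of causality.

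The analysis follows the body text. Section 8.6.2: "A treatment-emergent AE will be defined as any AE that begins on or after the date of first dose of study drug", with the period closing at last dose plus 70 days (±7). Sections 8.3.1.2 and 8.6 use the same limit for the safety summaries.

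Sections 3.6 and 6.12 state that patients are followed for AEs as Appendix Table 9 specifies.

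**The concern.** A site that opens the post-treatment schedule finds an instruction to narrow its reporting partway through follow-up. A site that opens Section 7 finds an instruction not to narrow it. Both are following the protocol, and Sections 3.6 and 6.12 give the first site a positive reason to rely on the table.

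Treatment-emergent AE incidence is part of the primary endpoint of the safety run-in cohorts and is the secondary safety endpoint of the Phase 2 cohorts. It is reported as a number and percentage of patients, so an event that was never recorded counts as no event. The study has no reference therapy, so no control arm would share the under-capture. The footnote also makes SAE collection after the first call depend on the investigator's view of relatedness, which Section 7.3.3 rules out.

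**Working it through.** **1. Which contact does the footnote mean?** There are two candidates.

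- 30-day contact: all AEs to Day 30, then only treatment-related SAEs from Day 30 to Day 70. Every word of the footnote has a function.
- 70-day contact: all AEs to Day 70, then treatment-related SAEs from Day 70 to Day 70. The second clause covers no time.

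Only the first is workable.

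**2. What each rule collects between the two contacts**

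| Event type | Footnote f | Sections 6.5.7, 7.3.2, 7.3.3 | In the analysis window (8.3.1.2, 8.6, 8.6.2) |
|---|---|---|---|
| Treatment-related SAE | yes | yes | yes |
| Unrelated SAE | no | yes | yes |
| Non-serious AE, related or not | no | yes | yes |

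**3. Fit with the rest of the table.** The AE row is ticked at Day 70 without restriction. Footnote a, attached to both safety columns, asks for a site visit after a treatment-related AE, or after an SAE whatever its attribution. Footnote f therefore sits badly with its own table as well as with the body text.

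**4. Size.** The plan states no figure to reproduce. The inputs are the contact days and ±7-day windows in Appendix Table 9: first contact on Day 23, 30 or 37, second on Day 63, 70 or 77.

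Restricted share = (second contact day − first contact day) / second contact day.

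| First contact | Second contact | Restricted days | Share |
|---|---|---|---|
| 23 | 63 | 40 | 63.5% |
| 23 | 70 | 47 | 67.1% |
| 23 | 77 | 54 | 70.1% |
| 30 | 63 | 33 | 52.4% |
| 30 | 70 | 40 | 57.1% |
| 30 | 77 | 47 | 61.0% |
| 37 | 63 | 26 | 41.3% |
| 37 | 70 | 33 | 47.1% |
| 37 | 77 | 40 | 51.9% |

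At the nominal days, (70 − 30)/70 = 40/70 = 57.1%. The range is 26/63 = 41.3% to 54/77 = 70.1%, and the share exceeds one half in 7 of the 9 combinations. With the footnote aligned to Sections 7.3.2 and 7.3.3, the restricted period is 0 of 70 days.

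**The case against.** The best defence is that one footnote departs from a design stated consistently elsewhere. Sections 6.5.7 and 7.3.2 order collection to Day 70 in plain terms, the table ticks AEs at Day 70, and footnote a covers SAEs of any attribution at both calls. Many sites will do the right thing. That stands, and it limits the consequence to possible inconsistent capture. It does not remove the conflict, because footnote f qualifies the very row that carries the Day 70 tick.

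A reader might infer four stronger things that the protocol does not support.

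- *That the footnote controls data capture.* Section 9.1.7 says "The eCRF casebook will only capture the data required per the protocol schedules of assessments". But the schedule in question ticks AEs at Day 70, and Section 9.1.7 does not say that a footnote overrides its own row or Section 7. The eCRF and its completion guidelines are not available to settle the matter.
- *That unrelated SAEs will go unreported.* Section 7.3.3 requires them. Section 7.4.1.1 requires transmission within 24 hours through the post-treatment follow-up period, and Section 7.1.2.1.1 requires deaths not due to AML progression to be reported whatever their attribution. A site would have to set aside several explicit rules, so inconsistent reporting is as far as the text goes.
- *That dose selection or the efficacy endpoint is compromised.* DLTs have their own assessment period counted from the start of treatment: 28 days, extended to 42 for prolonged myelosuppression in Cohorts 1 and 2. Section 8.3.1.2 bases the recommended Phase 2 dose on the DLT Evaluable Analysis Set. The CR rate does not use these data.
- *That more than half of the window is always at stake.* This is true at the nominal days but not across the permitted visit windows.

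**Conclusion.** This is an internal contradiction in current text, and footnote f is wrong as written. It restricts reporting over nominally 40 of the 70 post-treatment days (57%; 41% to 70% with the visit windows), during which the body text collects, and the analysis counts, all AEs and SAEs.

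The likely harm is uneven capture of non-serious AEs and unrelated SAEs between sites, with a possible downward bias in descriptive treatment-emergent AE incidence. How many events would be missed cannot be derived from the protocol. It depends on how many sites follow the footnote and on the event rate in that period, and neither is given. The percentages therefore measure the length of follow-up in dispute, not the share of events lost. They rest on reading the footnote's first contact as the 30-day one, which is the only reading that leaves its second clause any content.

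**What to change.** Replace footnote f of Appendix Table 9 with: *Report all AEs and all SAEs, regardless of relationship, through the 70-day (± 7 days) safety follow-up visit/call.* This matches Sections 6.5.7, 7.3.2 and 7.3.3 and the window in Section 8.6.2. Confirm that the eCRF and its completion guidelines ask for the same.

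The cost is one footnote in the next amendment, a short memo to sites and a few more AE entries per patient. No visit is added, because the Day 70 contact is already scheduled.
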